15. Data/sample storage for future use.....	23
16. Data analysis and monitoring.....	23
17. Data analysis plan	23
17.1 Sample size determination	23
17.2 Statistical analysis	24
17.3 Quality control	24
17.4 Missing data	24
10. References.....	24

Figure 1. Study Schema

1. Purpose of the study

In this study, the feasibility of delivering a time-restricted eating (TRE) intervention among fatigued cancer survivors will be assessed. The participants will be asked to eat *ad libitum* only within a self-selected 10-h window each day for 14 days, and exploratory measures of fatigue, well-being, and other symptoms will be collected at baseline and post-intervention. These feasibility data will be used as preliminary data for a grant proposal addressing one of NCI's Provocative Questions: "How does intermittent fasting affect cancer incidence, treatment response, or outcome?"¹

The feasibility of conducting a 10-h TRE intervention among cancer survivors will be evaluated using the following specific aims:

Primary Aim: to assess the adherence of the participants to the 10-h TRE intervention. This will be determined by the percent of days that each participant adheres to the 10-h TRE dietary pattern over the course of the 14-day intervention.

Secondary Aim 1: to assess the retention of participants during the 10-h TRE intervention. This will be determined by the percent of consented participants who provide baseline and post-intervention assessments.

Secondary Aim 2: to assess the safety of the TRE intervention. We will closely monitor instances of adverse events as described by the Common Terminology Criteria for Adverse Events (CTCAE), version 5,² with a special focus on body weight.

Secondary Aim 3: to describe the feasibility of recruiting cancer survivors to a 10-h TRE intervention. The number consented over the number approached will be calculated, and the population (i.e., those approached) will be characterized based on eligibility and willingness to participate.

2. Background and rationale

Cancer-related fatigue affects at least 30-90% of patients undergoing chemotherapy, depending on the type of cancer and treatment as well as the diagnosis method.^{3,4} It is not relieved by sleep or rest, and its severity can greatly hinder the ability to perform activities of daily living and decrease quality of life. The mechanisms behind the etiology and pathophysiology of cancer-related fatigue seem to be related in part to inflammation, hypothalamic–pituitary–adrenal (HPA) activation dysfunction, metabolic and/or endocrine dysregulation, or other mechanisms, but are largely not understood, thereby thwarting the development of effective preventative strategies and treatments.⁵

Circadian rhythms are biological diurnal cycles that work in synchrony to regulate hormone secretion, the sleep/wake cycle, core body temperature, and other processes. Circadian rhythm and human health have a bidirectional relationship, and circadian disruption is associated with a broad range of pathologies including, purportedly, cancer-related fatigue.⁶⁻⁸ Circadian regulation occurs via genetic and physiological processes, and is important to maintain homeostasis of the endocrine system, autonomic nervous system, and nutrient metabolism.^{9,10} The importance of maintaining circadian rhythm is clear when traveling across time zones, and "jet lag" is a common experience of fatigue when the circadian clock is disrupted.¹⁰ Our group (Division of Cancer Control) has demonstrated that chemotherapy disrupts circadian rhythm, and that changes in circadian rhythm are associated with fatigue.⁸ Further, research from our group has shown that yoga can help regulate biobehavioral oscillations of circadian rhythm and, consequentially, improve sleep and reduce fatigue.¹¹

Regulation of circadian rhythm relies heavily on regular sleep habits, and interventions to regulate circadian clock currently include light therapy, exercise, melatonin supplementation, and more recently,

nutrient timing.¹⁰ Indeed, there are consistent animal and human data demonstrating that aberrant feeding/eating patterns dysregulate objective circadian clock measures (i.e., expression of genes that show strong diurnal oscillations).¹² In an observational study among 156 healthy American adults in California, Gill and Panda¹³ showed **that approximately 50% of people eat within a window greater than 14.75 hours per day**; only 10% eat within a window 12 hours or less.⁹ It is unknown but likely that eating patterns are similar among American cancer survivors. A consistent, shorter window of eating, for example 10 hours or shorter, may aid in the regulation of the circadian clock and improve metabolic homeostasis with broad health outcomes.^{9,14,15} Restricting eating to certain time window is called “time-restricted eating” (TRE).

TRE as a therapeutic approach has garnered a large appreciation in the literature and in the public in the last decade for its ability to mediate the circadian clock and prevent and treat various pathologies.^{14,15} TRE involves restricting the consumption of calories to a short window (4-12 hours) during normal waking hours, for example 8am-6pm; water is never restricted. Human (time-restricted eating) and rodent (time-restricted feeding) studies have shown that TRE helps to maintain metabolic homeostasis and, as a result, prevents excess body weight, improves sleep, and attenuates age- and diet-induced heart disease (review¹⁵). One study clearly demonstrated the effects of nutrient timing on metabolic regulation: time-restricted feeding vs. time-unrestricted feeding of mice led to weight loss despite equal energy intake.¹⁶ In humans, Gabel et al. performed an 8-h TRE study among obese adults for 12 weeks (n=23).¹⁷ Despite the diet being *ad libitum*, caloric intake decreased 341 ± 53 kcal/day. Body weight decreased $2.6 \pm 0.5\%$, and systolic blood pressure decreased 7 ± 2 mmHg. However, there were no significant changes in body composition, circulated lipids, fasting blood glucose, or fasting insulin. Also, Wilkinson et al. performed a 10-h time restricted eating study among patients with metabolic syndrome for 12 weeks (n=19).⁹ They observed improvements in sleep efficiency and quality, a safe rate of decrease in body weight and body fat percentage, a reduction in total and low density lipoprotein (LDL) cholesterol, and reductions in systolic and diastolic blood pressure.⁹ While these studies were implemented for 12 weeks, benefits have been seen in glucose and lipid metabolism and circadian clock gene expression in as short as 4 days.¹⁸

To date, TRE has only been studied in healthy participants or those who are overweight, obese, or with metabolic syndrome (Wilkinson et al.⁹ and references within). These studies have collectively shown that a 10-h TRE window is feasible, safe, and effective at improving metabolic markers among their respective populations. Thus, the next logical step is to prudently begin to apply a dietary pattern intervention to cancer survivors with the ultimate goal of evaluating its effectiveness to treat cancer-related fatigue. Thus, herein, a single-arm pilot TRE study will be conducted among cancer survivors to assess the feasibility of recruiting participants to a TRE intervention and adherence of survivors to a 10-h TRE window for 2 weeks. These data will serve as preliminary data for an R21 grant application in response to a Provocative Question posed by the NCI: “PQ2: How does intermittent fasting affect cancer incidence, treatment response, or outcome?”¹ If this single-arm pilot study is successful, the grant application will propose a randomized controlled trial evaluating the preliminary efficacy of TRE vs. longer eating windows to alleviate cancer-related fatigue among cancer survivors.

3. Administrative organization

We will be recruiting subjects from the Wilmot Cancer Institute. Participants will be approached in the oncology clinics where cancer survivors have routine follow-up appointments. Alternatively, patients referred to the study team by the treating provider may be called, emailed, or sent a letter giving them basic information about the study. These clinics include Wilmot Cancer Institute, Pluta Cancer Center, or another Wilmot satellite location. Private areas in any of these locations may be used to consent the participant and

do study assessments. Participants will also be asked to complete some of the assessments at home. As an alternative to clinic visits, this entire study can be completed remotely.

4. Study design

4.1 Brief description and specific aims

This will be a single-arm feasibility pilot study among 40 cancer survivors with moderate to severe baseline fatigue. All participants in this study will be asked to follow a TRE meal pattern for 14 consecutive days. Participants will be encouraged to consume food and beverages only within a 10-h time window for the 14-day intervention, with the exception of water, which will be encouraged at any time. Participants will be allowed to take any of their normal medications at the prescribed times. Participants will be asked to complete a daily diary (every day for 14 days, approximately 1 min each day), as described in §4.4. At baseline, mid-point, and post-intervention, participants will be asked to record their body weight with a scale that the study team will provide. Also at baseline and post-intervention, participants will complete questionnaires related to their fatigue, quality of life, symptoms, and a 24-h food recall (approximately 10 min). Post-intervention, we will conduct an exit interview with each participant about their experience with the intervention (10-30 min).

Primary Aim: to assess the adherence of the participants to the 10-h TRE intervention. This will be determined by the percent of days that each participant adheres to the 10-h TRE dietary pattern over the course of the 14-day intervention.

Secondary Aim 1: to assess the retention of participants during the 10-h TRE intervention. This will be determined by the percent of consented participants who provide baseline and post-intervention assessments.

Secondary Aim 2: to assess the safety of the TRE intervention. We will closely monitor instances of adverse events as described by the Common Terminology Criteria for Adverse Events (CTCAE), version 5,² with a special focus on body weight.

Secondary Aim 3: to describe the feasibility of recruiting cancer survivors to a 10-h TRE intervention. The number consented over the number approached will be calculated, and the population (i.e., those approached) will be characterized based on eligibility and willingness to participate.

4.2 Participant population

In total, 40 cancer survivors will be recruited. Participants will be recruited from Wilmot Cancer Institute including satellite clinics (e.g., Pluta Cancer Center) and will have medical clearance from their provider. From previous local studies completed by the Division of Cancer Control, a 20% rate of attrition is expected, resulting in approximately 32 participants with evaluable data.

No special classes of participants such as fetuses, neonates, children, pregnant women, prisoners, institutionalized individuals, or decisionally impaired adults will be recruited.

Total planned enrollment: 40 participants

Targeted/planned enrollment by ethnic and racial categories:

Ethnic Category	Sex/Gender		
	Females	Males	Total
Hispanic or Latino	2	1	3
Not Hispanic or Latino	25	12	37
Ethnic Category: Total of All Participants	27	13	40
Racial Categories			
American Indian/Alaska Native	0	0	0
Asian	1	1	2
Native Hawaiian or Other Pacific Islander	0	0	0
Black or African American	2	2	4
White	24	10	34
Racial Categories: Total of All Participants	27	13	40

Males and females will be recruited to this study. However, there is an expectation to recruit more females than males because Pluta Cancer Center will be a major recruitment site and Pluta houses the Comprehensive Breast Care program. Based on the participant characteristics of recently completed local studies by our Division, it is anticipated that the potential sample pool for the current study will be mostly white/non-Hispanic individuals, though participants of other racial and ethnic groups will be encouraged to participate. The average age for studies conducted by our Division tends to be approximately 55-65 years, and it is expected to be similar for this study, too. Children, individuals under the age of 18, as defined by the NIH Grants Policy Statement, will not be included because their meal timing is often determined by their parents/guardians/caregivers.

4.3 Study interventions

This will be a single-arm, feasibility pilot study that recruits 40 cancer survivors. After screening and consent, participants will complete an on-study form and baseline questionnaires: the Functional Assessment of Chronic Illness Therapy (FACIT-F), Brief Fatigue Inventory (BFI), the 27-item modified MD Anderson Symptom Inventory, and a 24-h Estimated Food Record. These questionnaires can be completed either online via REDCap or on paper (participant's choice) and take less than 10 min total to complete. Participants will be provided with a small bathroom scale, with which they will be asked to report their weight at baseline (Day 1), mid-point (Day 8), and post-intervention (Day 15). We prefer that body weight is measured at home, in the morning, before food or drink is ingested, without clothing. Before the intervention period, all participants will be instructed as to how to follow a TRE diet pattern. The TRE window will be 10 hours long and will be selected by the participant based on their normal meal patterns and preferences. For example, the window could be 7am-5pm, 8:30am-6:30pm, or 12:00pm-10:00pm. However, the window should not change during the intervention period. Every day for 14 days, participants will be asked to consume food and beverages only within the 10-h window; water will be allowable any time. Because of the potential of caffeine and artificial sweeteners to affect circadian rhythm,^{19,20} coffee, tea, chewing gum, and diet beverages will be discouraged during the fasting window. Also for these 14 days, participants will complete a daily diary at the end of the day noting the time they wake up, the time

of their first calorie, the time of their last calorie, the time they go to bed, and their average fatigue level for the day.

There will be an emphasis on honesty over adherence, and participants' experiences will be used to improve the intervention in a larger, future study. Post-intervention, the participants will be asked to complete the same questionnaires as baseline (i.e., FACIT-F, BFI, Symptom Inventory, 24-h Estimated Food Record), and body weight will be measured. An exit interview will be conducted to assess what the participants did and did not like about the intervention; if they think it improved their symptoms, sleep quality, or quality of life; what tips they have for future participants; if they would recommend the eating pattern to friends; or any other constructive comments. This interview will last 10-30 min, and it will be audio-recorded with explicit permission.

Participants will have the option of completing all the questionnaires and daily diaries electronically or on paper. Similarly, exit interviews can be completed on-site or via phone according to patient preference. Participants will be compensated for their time \$10 for baseline assessments, \$10 to complete daily diaries, and \$10 for post-intervention assessments for a total of \$30 maximum.

All questionnaires will be scored and entered into a secure database by the study team. Adherence will be the primary end-point; it is expected that participants will be able to eat within the 10-h window at least 5-6 out of 7 days per week,^{17,21} or 11/14 days (78.6% adherence). In regard to retention, we expect that at least 32/40 (80%) of participants who complete baseline assessments will complete post-intervention assessments. Changes in quality of life and fatigue will be assessed over time as exploratory measures.

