4.4 Study outcomes/endpoints

The primary aim of this study is adherence, as assessed using daily diaries. How many days the participants were able to restrict their eating to the 10-h window will serve as the primary endpoint. The daily diary will include the time of the first calorie consumed and the time of the last calorie consumed every day for the 14-day intervention. Success will be defined by the participants reaching the fasting target at least 11 of the 14 days on average. This goal is reasonable based on a study by Kesztyüs et al.,²¹ whose participants adhered to this dietary pattern $85.5 \pm 15.2\%$ of days over a three-month intervention, and a study by Gabel et al.,¹⁷ whose participants adhered 5.6 ± 0.3 days/week (80%) for 12 weeks on average.

A secondary aim is retention; it is expected that at least 80% (32 out of 40) of those who provide baseline data also provide post-intervention data.

Another secondary aim will be safety. We hypothesize that body weight will be maintained within 5% of baseline throughout the intervention and that there will be no adverse events that are Grade 2 or worse that are attributable to the intervention.² To ensure safety in regard to weight loss, body weight will be measured three times: baseline (Day 1), mid-point (Day 8), and post-intervention (Day 15). Body weight will be measured by the participant by a scale that is provided, and then reported on the daily diary (e.g., BalanceFrom Digital Body Weight Bathroom Scale). To ensure consistent and reliable measures, participants will be asked to weigh themselves in the morning, before eating or drinking, with minimal clothing. The scale should be placed on a hard, level surface (e.g., tile, wood) that is the same for each measurement, if possible, because there can be slight variations in measurements if the scale is placed on a rug vs. a hardwood floor, for example. Participants will have the option of keeping the scale at the end of the study.

To ensure safety in regard to adverse events, we will closely monitor all adverse events as described by the CTCAE, version 5.² Adverse events that will be of particular interest due to potential causality include weight loss or weight gain (see §9.1.1), dizziness, and exacerbation of fatigue.

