8.2.5 Schedule of assessments

After consenting to the study, the participant can decide to start the intervention any day within the next week. Preferably, the 24-h Food Record and baseline questionnaires will be performed the day before the intervention begins (Day 0) and body weight will be measured on the first day of the intervention (Day 1), but participants will be given up to 3 days to begin in case there are technical difficulties with REDCap or other barriers to starting the intervention. Similarly, it is preferred that post-intervention questionnaires are completed the day after the intervention ends (Day 15), but up to 3 days will be allowed. On Day 8, the participant will provide body weight. The Day 14 24-h Food Record should be performed on Day 14, but can be completed on Day 12, 13, or 14 if there are anticipated logistical reasons why completion of the diary on Day 14 would not be possible. Post-intervention exit interviews will be performed with a member of the study team within one week of completing the intervention. Participants will be asked to complete the daily diaries every day at the end of the day.

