8.2.7 Data collection tables

A Clinical Record form will be completed by the study team using the medical record. These following table lists study-related activities that the participants will experience.

Assessment or Activity	Study Goal	Assessment Location	Baseline (approx. Day 0)	Intervention Day 1	Intervention (Day 1-14)	Intervention Day 8 (approx.)	Intervention Day 14 (approx.)	Post-intervention (approx. Day 15)
On-study data form	Demographics and clinical characteristics	Clinic or home (REDCap*)	✓					
24-h Food Record	Safety	Home	✓				✓	
Functional Assessment of Chronic Illness-Fatigue (FACIT-F)	Exploratory	Clinic or home (REDCap*)	✓					✓
Brief Fatigue Inventory (BFI)	Exploratory	Clinic or home (REDCap*)	✓					✓
Symptom inventory	Exploratory	Clinic or home (REDCap*)	✓					✓
Body weight	Safety	Clinic or home		✓		✓		✓
Daily diary	Primary aim	Home (REDCap*)			Every day, at the end of the day			
Check-in	Check-in	Remote				✓		
Exit interview	Exploratory	Clinic or home (telephone)						✓

*If a participant prefers, they may complete paper-based versions of these assessments and return them to the study team in-person or in a postage-paid envelope.

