9.1.2 Hunger and hunger-related symptoms due to the intervention

For most participants, eating within only a 10-h window will mean re-adjusting their typical eating pattern. Many participants will need to rearrange their meal times—either delay breakfast or eat dinner earlier. If they delay breakfast, they might feel hungry in the few hours leading up to their eating window, especially in the first few days of the study. Similarly, they might crave something before bed if they are in the habit of eating before bed. With hunger can come lack of concentration, fatigue, dizziness, irritability, and other symptoms. All participants will be encouraged to stay hydrated and to consume a snack outside of the window if symptoms become debilitating.

Probability: Moderate

Magnitude: Low to moderate

Duration: Short-term

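### The end-of-day adherence diary has no item or rule for calories taken after the entry, so out-of-window eating later that evening can go unrecorded and raise the adherence count

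*Combined protocol and SAP*

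**What the plan says.** Section 4.4 names the diary as the source of the primary endpoint: "The primary aim of this study is adherence, as assessed using daily diaries". It lists the times of the first and last calorie as the diary content on which adherence rests. The success rule is in the same section: "Success will be defined by the participants reaching the fasting target at least 11 of the 14 days on average". Section 17.2 repeats it.

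The timing of the diary is consistent throughout. Section 4.3 says that "participants will complete a daily diary at the end of the day noting the time they wake up, the time" and then names the other items: first calorie, last calorie, bedtime and the day's average fatigue. Section 8.2.5 says "Participants will be asked to complete the daily diaries every day at the end of the day", and the section 8.2.7 table, which labels the diary as serving the primary aim, says "Every day, at the end of the day". No clock time is given. No section provides for a next-morning check or for correcting an entry, and the listed items include no question about eating after the previous entry.

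The protocol expects or allows some eating outside the window. Section 9.1.2 says of participants that "they might crave something before bed if they are in the habit of eating before bed" and encourages a snack outside the window if symptoms become debilitating. Section 9.1.3 tells participants that deviations are permitted, and section 9.1.1 affirms their right to eat outside the window.

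**The concern.** A same-day entry that also asks for bedtime will usually be made before the participant is asleep. Some interval therefore remains between the entry and sleep, and its length is left open. If the participant eats in that interval, outside the window, on a day that was otherwise adherent, the recorded last-calorie time is too early and the day is counted as adherent. An honest participant has no stated place to report the later snack.

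The error has one direction. Missing a late calorie can turn a non-adherent day into an adherent one, but not the reverse. The success rule is a single threshold on the mean number of adherent days, so any such error favours declaring the intervention feasible. That result is meant to support a grant application for a randomised trial.

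**Working it through.** **The plan's own figures.** The threshold is 11/14 = 0.7857, which agrees with section 4.3, "11/14 days (78.6% adherence", and with the rounded 79% in section 17.2. Section 4.4 cites two benchmarks. One is 5.6 days per week (80%), or 5.6 × 2 = 11.2 days of 14. The other is 85.5% of days, or 0.855 × 14 = 11.97 days. The lower benchmark is 11.2 − 11 = 0.2 days above the threshold.

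**Model.** Let T be the true mean number of adherent days out of 14. Let f be the share of non-adherent days whose only breach comes after the diary entry and is therefore missed. The recorded mean is

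R = T + f × (14 − T).

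The documents give no value for f, so every value below is an assumption. The model takes all 14 diaries as complete and includes no other reporting error.

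**Share that would have to be missed to record exactly 11:** f = (11 − T)/(14 − T).

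| True mean T | 14 − T | f needed |
|---|---|---|
| 10.5 | 3.5 | 0.5/3.5 = 14% |
| 10.0 | 4.0 | 1.0/4.0 = 25% |
| 9.0 | 5.0 | 2.0/5.0 = 40% |

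For scale, with the 32 evaluable participants expected in section 17.1 and T = 10.5, there would be 32 × 3.5 = 112 non-adherent days. Recording a mean of 11 needs 32 × 0.5 = 16 of them to be missed.

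**What a recorded mean of 11 could represent:** T = (11 − 14f)/(1 − f).

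- f = 5%: 10.3/0.95 = 10.84 days
- f = 10%: 9.6/0.90 = 10.67 days
- f = 20%: 8.2/0.80 = 10.25 days

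**At the cited benchmarks.** With T = 11.2 or 11.97 the target is met at f = 0. Missed late eating would raise the reported mean (at T = 11.2 and f = 10%, by 0.1 × 2.8 = 0.28 days) but would not change the success conclusion.

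**The case against.** The strongest reply is that a diary asking for the last calorie and bedtime is naturally completed at bedtime, when eating is over. The example windows in section 4.3 close at 5pm, 6:30pm and 10pm, so on most days the last calorie is already past. This stands as far as it goes: the documents do not show that entries precede the last calorie. It describes adherent days best, however. The exposed days are those on which the participant eats after the window has closed, and nothing fixes the entry after that point.

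There are partial safeguards: honesty is put ahead of adherence (section 4.3), payment is for completing diaries rather than for adhering (section 12), a mid-point contact asks how the diaries are going (section 14.3), and a timed food record is kept on or near Day 14 (sections 4.4 and 8.2.5). They lower the general risk of misreporting. None collects post-entry eating, and the food record covers one day, is listed for safety, and is not assigned to check the diary.

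A reader might infer more than the documents support:

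- **That adherence is overstated.** No rate of post-entry eating is given, so only the possibility and its direction are established. The direction is clear for eating before midnight. A snack after midnight may be entered as the next day's first calorie and count against that day.
- **That the missed interval is when the window is most likely to be broken.** Section 9.1.2 mentions craving before bed, but it also names hunger in the hours before the window opens, which an evening entry captures.
- **That an anticipated bedtime harms the endpoint.** Adherence rests on first- and last-calorie times, and section 17.2 makes no use of bedtime.

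**Conclusion.** The point holds as a minor gap in how the primary endpoint is measured. The only stated source of adherence is completed on the same day, and no listed item or rule captures calories taken afterwards. Out-of-window eating between entry and sleep on an otherwise adherent day can go unrecorded, and that error can only raise the count.

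Its size cannot be estimated from the documents. It would affect the success decision only if the true mean lay somewhat below 11 days: about 14% of non-adherent days would have to be missed at a true mean of 10.5, and 25% at 10.0. A result near the threshold is plausible, because one cited benchmark is only 0.2 days above it, but at either benchmark the decision is unaffected. The conclusion assumes that the diary holds only the items section 4.3 lists; the form itself is not part of the documents.

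**What to change.** Keep the evening diary and add one item to the next day's entry, for example: *Did you consume anything other than water after yesterday's entry? If so, at what time?* Day 14 has no following diary entry, so put the same item in the Day 15 post-intervention questionnaires. Refer there to Day 14 explicitly, because section 8.2.5 allows those questionnaires up to 3 days late.

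In section 17.2, state that the answer updates the earlier day's last-calorie time before that day is scored. Because the endpoint concerns calories, the update should apply only where calories were consumed. State also which day a post-midnight snack belongs to, so that it is not counted against two days. Sections 4.3, 8.2.5 and the section 8.2.7 table need matching wording.

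The cost is one short extra question per day. Moving the whole diary to the next morning is not needed. It would add overnight recall of first-calorie time and fatigue, and it would disturb the Day 1 and Day 8 weights that section 4.4 has participants report on the diary.
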